Figure 2. Randomization Flow Chart

Appendix 1.1

Adaptive Study Design

We propose to complete the current study as planned until the target sample size is reached. Statistician [name] will then unblind the treatment allocation (identify who is in group A vs B but not identify the groups themselves as active drug or placebo) and analyze the data to determine whether a significant treatment effect was observed. If the p value is significant ($p<0.05$) [name] will complete the analysis as outlined in the Statistical analyses section.

If the p value is not significant ($p>0.05$), [name] will re-calculate the sample size based on the observed data from 84 participants, in order to determine what sample size is required to observe a statistically significant effect. This data will be provided to the DSMB who will decide whether or not to continue the study, based on feasibility and the clinical relevance of the treatment effect size. If the DSMB decides it is feasible and the treatment effect is clinically relevant, the study will be continued until the new re-calculated sample size is reached and all study site investigators and personnel will remain blinded to treatment allocation. Additional study sites may be added and further funding may be sought for the extension study. The data collected as part of this current study will be used in the extension study. The extension study will be designed as an adaptive trial (52). Adaptive trial designs are study designs that allow for adaptations to be made to the trial after its initiation without undermining the validity and integrity of the results (53). They are increasingly being used to study rare diseases in which there are limited numbers of subjects and trial durations are frequently very long. The significance level (i.e. p value) of the extension study will be adapted to adjust for the fact that unblinded analysis was conducted at the end of this current study(54).

Appendix 1.2

Data Safety Monitoring Plan

Although subjects will be randomized to either oral prednisone or placebo, no investigational drug will be tested in this trial. Upon funding of the study, the study will be submitted to the Research Ethics Board (REB) at the Hospital for Sick Children and all other study sub-sites). REB comments and amendments will be distributed to all sites in order to ensure that the approved study protocol is identical at all sites.

Assessment of Risk

The assessment of risk is deemed to be **moderate** in this trial due to the known side effects of prednisone (eg. hyperglycemia, hypertension, gastrointestinal bleeding). Given that we will be treating subjects with a short course of oral prednisone (7 days), we do not expect to observe the long-term side effects noted with more prolonged steroid use (eg. growth retardation, osteopenia/avascular necrosis). Although certain subjects will receive placebo, they will still be receiving antibiotic treatment for the pulmonary exacerbation which is standard of care.

Anticipated Adverse Events and Grading Scale

In the previous study by Dovey et al. 12 CF subjects received oral prednisone (2 mg/kg/day x 5 days) and 12 subjects received placebo during treatment for a pulmonary exacerbation (13).

The most common adverse events were glucosuria, hyperglycemia and hypertension.

Hypertension was reported for 2 subjects in each arm, with one prednisone treated subject withdrawn on day 2 due to this. Glucosuria was reported among 6 subjects in the prednisone arm and 1 in the placebo arm ($p=0.03$); 2 of the subjects in the prednisone arm with glucosuria also had hyperglycemia (1 of these was withdrawn due to this). Additional adverse events included headache, restlessness, heartburn, nausea/epigastric pain, swelling, increased thirst and increased urination. There were no serious events in either treatment arm.

We therefore anticipate the most common adverse events to be hyperglycemia (random serum glucose > 200 mg/dL or 13 mmol/L)(55), glucosuria ($> 1+$ urine glucose) and hypertension (defined as the 99th percentile of blood pressure measurement according to gender, age and

height using the NIH guidelines(56)) and will monitor for these adverse events (see below-Safety Monitoring Plan). In addition, all untoward medical occurrences, whether or not deemed causally related to study participation, will be recorded and site investigators will be asked to assess both severity and whether or not the adverse event was related to study participation. We will use the following grading scale to assess adverse events:

Adverse Event Category	Description
Mild	transient event, no treatment change, e.g. glucosuria
Moderate	treatment discontinued e.g. severe/sustained hypertension or hyperglycemia
Severe	severe: death, unexpected hospitalization

Given that subjects will be randomized at the time of hospitalization for a pulmonary exacerbation, we will monitor the time to subsequent exacerbation. If we observe a shorter time to subsequent exacerbation in one of the treatment arms, this will be reported to the DSMB.

Reporting of AEs

All adverse events will be recorded by the research coordinator and reported to the study site investigator as well as the PI ([name]), who will oversee close and continuous monitoring for safety concerns throughout the trial. All serious adverse events will be reported to Health Canada, based on the Health Canada Guidance: Adverse Drug Reactions (ADRs) Reporting Criteria. All serious and unexpected adverse events will also be reported to the REB at each study site as well the REB at the Hospital for Sick Children (as study sponsor) within 48 hours of their occurrence. Adverse events will also be reported to the Data Safety Monitoring Board (DSMB) (see below) in the form of regular reports submitted every 6 months. Serious adverse events will be reported to the DSMB within 48 hours.

Safety Monitoring Plan

Hospitalized subjects will be monitored on day 7, day 10 (+/- 2 days) and on day 14 with urine dip glucose measurements while on prednisone (or placebo). If the urine glucose is > 2+, a serum glucose measurement will be performed. All the information will be provided to the treating physicians; they can decide at any time to withdraw their patient and request unblinding of the treatment allocation. To unblind a subject, the research coordinator or physician will call the PI ([name]) at [contact] [name] or page [contact]

who will then request unblinding from the study data analyst. Additionally, subjects will also have a blood pressure done on day 7, day 10 (+/- 2 days) and on day 14 as part of their vital signs assessment. The research coordinator will also visit the subject daily to record all adverse events.

For patients who receive their treatment at home with home intravenous antibiotic therapy, they will be taught how to test their urine glucose (or parents in the case of children) on day 7, day 10 (+/- 2 days) and on day 14 and told to call the research coordinator with the result and report their adverse events. If the urine glucose is > 2+, they will be asked to come to clinic to have a serum glucose drawn and reported to the research coordinator as well as responsible physician. The home care nurse (or via home ambulatory machine) will also do the blood pressure check on day 7, day 10 (+/- 2 days) and on day 14 and report it to the research coordinator as well as responsible physician. The decision to withdraw a subject based on adverse events of hypertension or hyperglycemia will be made by the treating physician. Once the 7 days of treatment (prednisone or placebo) are completed, the subjects will be instructed to call the research coordinator with serious adverse events such as a re-hospitalization for a pulmonary exacerbation. At the follow up clinic visit, the research coordinator will once again review adverse events with the subject.

Diabetic patients on insulin may have disruption of their glucose control while on prednisone. Therefore, as per standard clinical care, diabetic patients on insulin will do daily blood glucose monitoring and adjust their insulin accordingly as per published guidelines{Committee, 2018 #83}. This will be performed and monitored by the clinical team and treating physicians as per standard of care. Diabetic patients for whom glucose control has become unmanageable will be discontinued from the study as per the treating physician's assessment.

Safety Reviews

The conduct of the study will be monitored by an independent Data Safety Monitoring Board. We will appoint members, including CF physicians, from Canadian CF centers that are not participating in this trial. In addition, we will also appoint an independent statistician (not involved in this trial) to be on the DSMB. The DSMD will review safety reports on a semi-annual basis, or pre their requested frequency. Under the direction of the statistician on the DSMB, an interim analysis will be performed at the mid-way point of the trial (when 42 patients have been randomized (minimum 21 in each arm) and the primary outcome has been collected) to assess for safety. The DSMB can request unblinding of the data at any time. Serious adverse events will be reported to the DSMB by the PI within 48 hours of their occurrence. In addition,

all serious and unanticipated adverse events will be reported to the local REB as well as the REB at the Hospital for Sick Children with 48 hours of their occurrence, as stated above.

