This will be a randomized, double blind, placebo controlled trial of 7 days of oral prednisone in CF patients receiving IV antibiotic treatment for a pulmonary exacerbation at the Hospital for Sick Children, and multiple sub-sites, both adult and paediatric populations across Canada..

Eligible patients will be randomized over a recruitment period of 3 years. Each patient can only be randomized in the study once.

Study inclusion criteria

1. Diagnosis of CF by newborn screening or at least one clinical feature of CF, AND either (a) or (b) as follows:
 - a) A documented sweat chloride ≥ 60 mEq/L by quantitative pilocarpine iontophoresis
 - b) A genotype with two identifiable CF-causing mutations
2. Age > 6 years old.
3. Acute pulmonary exacerbation treated with IV antibiotics as previously defined
 - 10% relative drop in FEV₁ from baseline at the time of exacerbation
4. Informed consent by patient or parent/legal guardian
5. Ability to reproducibly perform pulmonary function testing
6. Ability to comply with medication use including the ability to take capsules, study visits and study procedures as judged by the site investigator

Study exclusion criteria

1. A respiratory tract culture positive for *Burkholderia cenocepacia* in the 12 months prior to enrollment
2. A respiratory tract culture positive for *Mycobacterium abscessus* in the 12 months prior to enrollment
3. Treatment with IV or oral corticosteroids within 2 weeks of enrollment or from Day 0-Day 7 of the pulmonary exacerbation
4. Active allergic bronchopulmonary aspergillosis (ABPA) at the time of enrollment as determined by treating physician
5. Asthma related exacerbation at enrollment as defined by the treating physician based on clinically compatible symptoms (eg. wheeze)
6. History of avascular necrosis or pathologic bone fracture
7. Uncontrolled hypertension with end organ damage
8. Active gastrointestinal bleeding
9. Status post lung or other organ transplantation
10. Pregnancy
11. Lactose intolerance (contained in placebo)
12. On Lumacaftor-Ivacaftor (Orkambi) at the time of exacerbation
13. Investigational drug use within 30 days prior to enrollment visit
14. Physical findings that would compromise the safety of the subject or the quality of the study data as determined by site investigator

D. Study protocol

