The questionnaire that will be used is the Cystic Fibrosis Questionnaire-Revised (CFQ-R) Respiratory domain (44). The CFQ-R is a disease-specific instrument that measures health-related quality of life for adolescents and adults with CF with a developmentally appropriate version for children. The CFQ-R is a reliable and valid measure of quality of life for individuals with CF and is frequently used in clinical trials to assess the effects of new therapies (45). In addition, subjects will also be asked to complete the CF Respiratory Symptom Diary (CFRSD) on day 0, day 7, day 14 and at the 1 month follow up visit(46). The Chronic Respiratory Infection Symptom Score will be applied to the CFRSD to calculate a severity score from 0-100 (100 being most severe). The CRISS score has been previously shown to be a responsive measure of steroid treatment effect in CF pulmonary exacerbations(47).

iv)The length of hospitalization and duration of IV antibiotic treatment in each treatment arm.

Length of hospitalization (number of days in hospital) and duration of IV antibiotic treatment are clinically relevant and patient-meaningful outcomes that will be calculated for each patient and compared between treatment groups.

v) The time to subsequent PEx in each treatment arm.

Based on our previous study, we know that the time between exacerbations is one of the most important determinants of overall lung function decline in an individual with CF (6). Time to subsequent pulmonary exacerbation will be calculated from the last day of IV antibiotic therapy of the randomized exacerbation to the first day of re-starting IV antibiotic treatment for a new pulmonary exacerbation (minimum 21 days between events). We will compare the average (or median if data not normally distributed) duration between treatment groups. We will follow up patients for subsequent exacerbations for 1 year following their randomized exacerbation.

vi) The number of adverse events and withdrawals from study recorded in each treatment arm.

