pulmonary function data points were available (n=228), we determined that 50% of patients will recover >90% of their baseline FEV₁ at day 7 of antibiotic treatment, with the remaining 50% available for randomization to either prednisone or placebo treatment. Of the 50% who do not recover >90% of baseline FEV₁ at day 7, 30% of these will go on to recover FEV₁ at day 14 of antibiotic treatment. We therefore estimated a 30% placebo response rate. Using these estimates, we calculated the sample size (**power two proportions** command in Stata 13.1) for the comparison of two proportions (Table 3).

For this study, we are aiming for a clinically significant treatment effect size of approximately two and a half-fold (30% response in the placebo arm vs 60% in the treatment arm). In order to have 80% power (at a significance level of 5%) we would need a sample size of **84 (42/arm)**. Estimating a 50% participation rate and a 20% drop out rate, we will need to approach 210 patients.

Since 50% of all patients who present with a PEx recover their lung function by day 7 of antibiotic therapy, 30% of patients will not experience more than a 10% relative drop in FEV₁ (inclusion criteria) and 10% of CF patients have diabetes and are on insulin which is an exclusion criteria (CPDR 2012 and personal communication-CF clinic directors), we will need to screen approximately 650 exacerbation events to approach 210 patients and enroll 105 patients into the study (Table 3). Over the 3 year study period, we expect to enroll enough study participants from all study sites) which will give us a sufficient population from which to enroll our necessary study sample size. We have had face to face meetings and discussions with our team of co-investigators who have been involved in the design and are fully committed to participating in this study. We have successfully collaborated with this team of researchers in previous clinical trials (10, 51) and fully expect we will achieve our current stated aims.

G. Statistical analyses

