When target sample size is reached, the study statistician (who will not be involved in the conduct of the study) will unblind the treatment allocation (identify who is in group A vs B but not identify the groups themselves as active drug or placebo) and estimate the treatment effect between the two groups based on the primary outcome (intention-to-treat). If there is a statistically significant treatment effect ($p<0.05$), the study statistician will do the following statistical analyses. For the primary outcome we will compare the proportion of randomized patients that responded at day 14 of therapy in the placebo arm compared with the treatment arm using a two sample test for proportions. We will perform intent-to-treat analysis according to the treatment arm subjects were randomized to. We will also perform a per-protocol analysis based on subjects who completed the 7 days of prednisone or placebo as per protocol. The same analysis will be performed for the proportion responding to therapy at 1 month. Logistic regression analysis will then be performed to adjust for potential confounders, such as age, gender, *Pseudomonas aeruginosa* or methicillin-resistant *Staphylococcus aureus* (MRSA) infection and lower FEV₁, as these factors have been associated with failure to recover lung function after an exacerbation (3, 25). For the additional secondary outcomes, absolute change in pulmonary function tests, length of hospitalizations and change in sputum measurements,

we will use parametric (t-test), or non-parametric (Mann-Whitney) two sample comparison test. Linear regression analysis will be then performed to adjust for potential confounders, as listed above. Time to subsequent exacerbation will be compared using a Cox proportional hazard model. Potential confounders will be adjusted for in the Cox-proportional hazard model. All secondary outcomes will be analyzed both as intention-to-treat and per-protocol. All outcomes will be obtained for all subjects irrespective of whether they completed the study per protocol. In the case of missing data, we will perform the analysis on complete (complete case analysis). To determine whether diabetic patients have a different response compared to non-diabetic patients, we will perform a sensitivity analysis comparing return to baseline lung function in diabetics vs non-diabetics according to treatment group.

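### Three minor text conflicts: two unequal glucose limits define hyperglycaemia, the sample size section uses a diabetes exclusion that is not in the eligibility list, and the dose-rounding phrase does not describe Table 1

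*Combined protocol and SAP*

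**What the plan says.** **Glucose.** Under Anticipated Adverse Events and Grading Scale, Appendix 1.2 lists "hyperglycemia (random serum glucose > 200 mg/dL or 13 mmol/L" among the three events it expects most often, with glucosuria (urine glucose above 1+) and hypertension. The Safety Monitoring Plan adds: "If the urine glucose is > 2+, a serum glucose measurement will be performed". Secondary outcome vi in Section E is "The number of adverse events and withdrawals from study recorded in each treatment arm".

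**Diabetes.** Section F, in building the screening total, says that "10% of CF patients have diabetes and are on insulin which is an exclusion criteria". None of the 14 items under Study exclusion criteria mentions diabetes or insulin. Section G plans a sensitivity analysis "comparing return to baseline lung function in diabetics vs non-diabetics according to treatment group", and the Safety Monitoring Plan says that "diabetic patients on insulin will do daily blood glucose monitoring and adjust their insulin accordingly".

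**Dose.** Section D gives prednisone at 2 mg/kg/day, up to 60 mg, with rounding to the nearest 10 mg, and refers to Table 1. The section on randomization and distribution has pharmacies dispense from Table 1. Its daily totals are 20 mg (10.0-14.5 kg), 30 mg (14.6-19.5 kg), 40 mg (19.6-24.5 kg), 50 mg (24.6-29.5 kg) and 60 mg above that.

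**The concern.** The glucose limit is an operative definition of a counted event. If the two units disagree, the same laboratory value can be an event at one site and not at another. Counts may be small: in the earlier randomised trial that Appendix 1.2 summarises, 2 of 12 prednisone patients had hyperglycaemia, so one relabelled patient would show. Section K makes the recommendation depend on prednisone patients not having more adverse effects, and foresees adding Canadian or US sites. Both are reasons to want a single definition.

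The diabetes clause contradicts three other parts of the protocol and is one of the stated inputs to the recruitment projection. It attributes a loss to an exclusion that does not exist. No loss is stated for the exclusions that do exist, for example "Treatment with IV or oral corticosteroids within 2 weeks of enrollment or from Day 0-Day 7 of the pulmonary exacerbation".

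The rounding phrase describes a dose rule that Table 1 does not follow.

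**Working it through.** **1. Glucose.** Input: molar mass of glucose 180.16 g/mol, so 1 mmol/L = 18.016 mg/dL.

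- 200 / 18.016 = 11.10 mmol/L.
- 13 x 18.016 = 234.2 mg/dL.
- Gap: 34.2 mg/dL, or 1.90 mmol/L.

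**2. Screening total.** Inputs from Section F: 30% v 60% response, 80% power, 5% significance (taken as two-sided), 20% dropout, 50% participation, 50% recovered by day 7, 30% without the required FEV1 drop, 10% for insulin-treated diabetes.

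The plan's own figures first:

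- Two proportions, no continuity correction: n per arm = [1.96 x sqrt(2 x 0.45 x 0.55) + 0.842 x sqrt(0.3 x 0.7 + 0.6 x 0.4)]^2 / 0.30^2, about 42. The total is 84, as stated.
- 84 / 0.8 = 105 to enrol, and 105 / 0.5 = 210 to approach, as stated.
- With all three screening percentages: 210 / (0.5 x 0.7 x 0.9) = 667. The plan says about 650, and 652 in Table 3. This is within 3%, but not equal.

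Without the diabetes factor the chain gives 210 / (0.5 x 0.7) = 600. The allowance implied by each row of Table 3, over and above the 50% and 30% losses, is:

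| Total N | Stated to screen | N / 0.8 / 0.5 / 0.35 | Implied further loss |
|---|---|---|---|
| 326 | 2,533 | 2,328.6 | 8.1% |
| 186 | 1,445 | 1,328.6 | 8.1% |
| 122 | 948 | 871.4 | 8.1% |
| 84 | 652 | 600.0 | 8.0% |

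All four rows carry a further loss of about 8%, not the 10% in the text. The documents do not show how that came about.

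The loss to the listed exclusions is not given. For an assumed 5%, 10% or 15%, the number to screen is 600 / 0.95 = 632, 600 / 0.90 = 667 or 600 / 0.85 = 706.

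**3. Dose.** Twice the weight, rounded to the nearest 10 mg, against the Table 1 daily total, in steps of 0.1 kg:

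| Weight (kg) | Nearest-10 rule (mg/day) | Table 1 (mg/day) | Table 1 at top of band (mg/kg/day) |
|---|---|---|---|
| 12.6-14.5 | 30 | 20 | 20 / 14.5 = 1.38 |
| 17.6-19.5 | 40 | 30 | 30 / 19.5 = 1.54 |
| 22.6-24.5 | 50 | 40 | 40 / 24.5 = 1.63 |
| 27.6-29.5 | 60 | 50 | 50 / 29.5 = 1.69 |

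Exact ties fall at 12.5, 17.5, 22.5 and 27.5 kg. Elsewhere in the bands below 29.6 kg the two agree, and Table 1 is never the higher.

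**The case against.** The strongest reply is that all of this is editorial, and much of that stands.

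- **Glucose.** No numerical action depends on the limit. Grades follow whether treatment was changed, withdrawal is the treating physician's decision, and "all untoward medical occurrences, whether or not deemed causally related to study participation, will be recorded". A serum test prompted by urine glucose above 2+ belongs to a patient who already meets the glucosuria definition. So the event label is at stake, not patient safety or data capture. A reader might infer that the label matters most for insulin users, whose glucose is checked daily. The documents do not support that: the definition rests on random serum glucose, while the daily checks are standard care run by the clinical team. Nor do the documents show which of the two figures was intended.
- **Screening.** The 650 is a feasibility projection. Recruitment runs until the target is reached, so it sets neither N nor power. A reader might infer that 650 is too high because a non-existent exclusion inflates it, or too low because the real exclusions are ignored. Neither can be shown, since the loss to the listed exclusions is not stated. It would also be too strong to say that the 10% produced the 650, because 10% gives 667.
- **Dose.** Section D itself points to Table 1 and pharmacies dispense from it, so no one has to choose between rules. The table is coherent on another reading: take weight to the nearest whole kilogram, double it, and round down to 10 mg. The 60 mg cap already gives heavier patients less than 2 mg/kg/day. A reader might also see a gap at exactly 29.6 kg, because the last band is printed with a strict inequality. That rests on one symbol which text extraction may have altered, and the pattern of the other bands puts 29.6 kg in the last one, so it is not claimed here.

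What survives is that the glucose definition is wrong as written, the diabetes clause conflicts with the rest of the protocol, and the rounding phrase misdescribes the table.

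**Conclusion.** Minor, but real on all three counts.

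1. The two hyperglycaemia limits differ by 34 mg/dL (1.9 mmol/L). The number of patients who will fall between them is unknown. The effect is confined to the hyperglycaemia count in secondary outcome vi and in the board's reports.
2. The diabetes exclusion in Section F does not exist in the eligibility list. The stated percentages give 600 without it and 667 with it; the printed 650/652 corresponds to an unexplained allowance of about 8%. Eligibility is unaffected if sites enrol from the exclusion list.
3. The rounding phrase overstates the Table 1 dose by 10 mg/day in four weight ranges below 29.6 kg. No dispensed dose changes.

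The 84 patients, the 210 to approach and the primary comparison stand. The unit conversion and the conflict over the exclusion need no assumption. The screening arithmetic takes the Section F percentages as given and multiplies them as independent factors.

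**What to change.** - **Appendix 1.2:** state one hyperglycaemia limit that agrees in both units, for example above 200 mg/dL (11.1 mmol/L). The sponsor should confirm which figure was meant.
- **Section F and Table 3:** delete the diabetes clause. Then either give 600 as the number to screen before any loss to the listed exclusions, or keep about 650 and say that it includes an allowance of about 8% for those exclusions. Explain the screening column of Table 3 in the same way.
- **Section D:** replace the rounding phrase with a statement that the dose is the one given in Table 1, with a target of 2 mg/kg/day and a maximum of 60 mg.

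The cost is a short wording amendment. It needs no extra patients, no new procedures, and no change to dispensing or to the analysis.
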